10.8.3 Maternal exposure

If a patient becomes pregnant during the course of the study, the IPs should be discontinued immediately.

Pregnancy itself is not regarded as an AE unless there is a suspicion that the IP under study may have interfered with the effectiveness of a contraceptive medication. Congenital abnormalities or birth defects and spontaneous miscarriages should be reported and handled as SAEs. Elective abortions without complications should not be handled as AEs. The outcome of all pregnancies (spontaneous miscarriage, elective termination, ectopic pregnancy, normal birth, or congenital

abnormality) should be followed up and documented even if the patient was discontinued from the study.

If any pregnancy occurs in the course of the study, then the Investigator or other site personnel should inform the appropriate AstraZeneca representatives within 1 day, i.e., immediately, but **no later than 24 hours** of when he or she becomes aware of it.

The designated AstraZeneca representative will work with the Investigator to ensure that all relevant information is provided to the AstraZeneca Patient Safety data entry site within 1 to 5 calendar days for SAEs and within 30 days for all other pregnancies.

The same timelines apply when outcome information is available.

10.9 FDA Reporting

When RPCI is the IND holder the following describes the FDA reporting requirements by timeline for AEs and new safety findings that meet the criteria outlined below:

Within 7 Calendar Days

Any adverse event that meets **ALL** the following criteria:

- Related or possibly related to the use of the study drug;
- Unexpected; and
- Fatal or life-threatening.

Within 15 Calendar Days

Any adverse event that meets **ALL** the following criteria:

- Related or possibly related to the use of the study drug;
- Unexpected; and
- Serious but not fatal or life-threatening;

Or, meets **ANY** of the following criteria:

- A previous adverse event that is not initially deemed reportable but is later found to fit the criteria for reporting (report within 15 days from when event was deemed reportable).
- Any findings from other studies, including epidemiological studies, pooled analysis of multiple studies, or other clinical studies conducted with the study drug that suggest a significant risk in humans exposed to the drug.
- Any findings from animal or in vitro testing that suggest a significant risk for human participants including reports of mutagenicity, teratogenicity, or carcinogenicity or reports of significant organ toxicity at or near the expected human exposure.
- Any clinically important increase in the rate of occurrence of a serious, related or possibly related adverse event over that listed in the protocol or investigator brochure.

Sponsors are also required to identify in IND safety reports, all previous reports concerning similar adverse events and to analyze the significance of the current event in the light of the previous reports.

Reporting Process

The principal investigator or designee will complete and submit a FDA Form 3500A MedWatch for any event that meets the above criteria. Forms will be submitted to the CRS QA Office via email to [contact]. Network sites: See Appendix A.

11 DATA AND SAFETY MONITORING

The Phase 1 portion of this study will be reviewed at the scheduled RPCI Early Phase Clinical Trial (EPCT) Program meetings and the minutes are forwarded to the IRB for review.

During the Phase II portion of this study, The RPCI Data, Safety Monitoring and Accrual Board (DSMAB) will assess the progress of the study, the safety data, and critical efficacy endpoints. The DSMAB will review the study annually and will make recommendations that include but not limited to; (a) continuation of the study, (b) modifications to the design, (c) suspension of, or (d) or termination of the study.

12 STATISTICAL METHODOLOGY

Phase I: The primary objective of the Phase I component of this study is:

- To assess the safety and toxicity of the combination of PARP inhibitor olaparib with anti-PD-L1 antibody durvalumab and anti-CTLA4 antibody tremelimumab

Phase II: The primary objective of the Phase II component of this study is:

- To assess the impact of the combination of olaparib with durvalumab and tremelimumab on PFS rates.

The secondary objectives of the Phase II component of study are:

- To assess the impact of the combination of olaparib with durvalumab and tremelimumab on anti-tumor immune responses in patients with recurrent platinum sensitive or resistant or refractory epithelial ovarian, fallopian tube, or primary peritoneal cancer who carry a germline and/or somatic BRCA1 or BRCA2 mutation.
- To assess the impact of the combination of olaparib with durvalumab and tremelimumab on PFS and/or OS in patients with recurrent platinum sensitive or resistant or refractory epithelial ovarian, fallopian tube, or primary peritoneal cancer who carry a germline and/or somatic BRCA1 or BRCA2 mutation.

12.1 Sample Size Determination

The potential Phase I study sample size ranges from a minimum of n=6 to a maximum of n=12. See Table 1 for the dose escalation schema. The Phase II portion of the study will have a sample

size of n=27. Subjects will be enrolled in the Phase II study at a ratio of 2:1 of platinum resistant to platinum sensitive disease.

Depending on the incidence of DLT(s), following a 3+3 design, the sample size is estimated to be 33 to 36 patients. Assuming the true DLT rate is much less than 1/3rd, we anticipate enrolling 36 subjects (9+27) where the accrual is expected to take up to 4 years.

12.2 Demographics and Baseline Characteristics

Descriptive statistics (as appropriate: n, percent, mean, median, min and max) will be used to summarize demographic and baseline characteristics.

12.3 Safety and Tolerability

The primary objective of the Phase I study is establishing safety. Assessment of safety and tolerability will be performed by the internal data safety monitoring panel on an ongoing basis, based on data review and regular conference calls with the investigators.

DLT: All patients who receive at least two cycles of durvalumab + tremelimumab and 8 weeks of olaparib treatment and respective safety assessments, as well as, all patients who discontinue the study prematurely due to DLT are considered fully evaluable per protocol for DLT (see Section 4.3 for patient replacement). Patients must also have received at least 75% of the planned dose of olaparib during the DLT evaluation period (except for patients who discontinued prematurely due to DLT) to be evaluable for DLT.

Safety set: All patients who received at least one dose of durvalumab + tremelimumab + olaparib will be evaluated for safety and tolerability.

Appropriate summaries of AEs, laboratory data and vital sign data will be presented. AEs will be listed individually per patient according to CTCAE version 4.03, and the number of patients experiencing each AE will be summarized using descriptive statistics.

The MTD is defined as the highest dose studied, for which the observed incidence of DLT is less than 33%. Frequencies of toxicities will be tabulated according to the National Cancer Institute Common Terminology Criteria for Adverse Events (CTCAE) version 4.03.

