4 METHODOLOGY

4.1 Study Design Overview

This is an open-label Phase I/II study for combination of the PARP inhibitor olaparib with anti-PD-L1 antibody durvalumab and anti-CTLA4 antibody tremelimumab, utilizing a 3+3 design. Fixed doses of durvalumab (1500 mg Q4W for up to 1 year) and tremelimumab (75 mg Q4W for 4 cycles) will be utilized with the recommended dose of olaparib for BRCA mutated ovarian cancer (300 mg BID for up to 1 year) in the first 6 patients in a Phase I safety run part of this study (Safety lead-in Cohort) followed by a Phase II part of the study (expansion cohort), enrolling 27 additional subjects. In case of >1 DLT out of the 6 patients, tremelimumab will be eliminated from this combination study as many of the toxicities from durvalumab and tremelimumab overlap but based on published studies, tremelimumab is associated with more frequent and severe side effects. Data suggested that increasing doses of durvalumab may not impact the safety of the combination as much as the tremelimumab dose. The dose of tremelimumab utilized here is the lowest effective dose and therefore de-escalation not recommended. If the DLT is olaparib related, de-escalation plan is to decrease to 250 mg and then to 200 mg as shown in **Table 1**, following the 3+3 rule.

Update: The Phase 1 portion of this study has been completed and reviewed. 6 patients were treated at Dose level -1 (durvalumab 1500 mg + tremelimumab 75 mg + Olaparib 250 mg) with no dose limiting toxicities observed. Based on this, the dose for the Phase II Expansion cohort was determined as **durvalumab 1500 mg IV Q4W up to 1 year + tremelimumab 75 mg IV Q4W 4 cycles + olaparib 250 mg PO BID up to 1 year**.

Table 1 Treatment of Algorithm on True DLT Risk**Phase I:**

Cohort	Dose Level	N	# of DLTs*	Action Based on # of DLTs			Total #	
Phase I Lead-in cohort	durvalumab 1500 mg + tremelimumab 75 mg + olaparib 300 mg	3	0, 1	+ 3	1/6 DLT: Phase II Expansion cohort		6 to 12 depending on DLTs	
			≥ 2	Eliminate tremelimumab: Phase II-T Expansion cohort or If DLT due to olaparib, dose de-escalate olaparib as follows:				
			+3		0/3 DLT: Phase II-O Expansion cohort: durvalumab 1500 mg + tremelimumab 75 mg + olaparib 250 mg			
			+3		1/3 DLT: +3 at same dose			
			durvalumab 1500 mg + tremelimumab 75 mg + olaparib 250 mg		1/6 DLT: Phase II-O Expansion cohort: durvalumab 1500 mg + tremelimumab 75 mg + olaparib 250 mg			

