4.3 Replacement of Participants

Patients who are not considered fully evaluable per protocol for the primary objective of safety and tolerability may be replaced. The period for evaluating DLTs will be from the time of first administration of durvalumab, tremelimumab, and olaparib until at least two cycles of durvalumab (8 weeks). Subjects who do not remain on the study up to this time for reasons other than DLT will be replaced with another subject at the same dose level. The compliance requirement for olaparib is 75% of the planned dose during the first 8 weeks. This applies to both Phase I and Phase II part of the study. There will be no replacement of patients during retreatment.

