6.4 Definition of Dose-Limiting Toxicity

Dose-limiting toxicities (DLTs) will be evaluated during the Phase I portion of the trial. The period for evaluating DLTs will be from the time of first administration of durvalumab, tremelimumab, and olaparib until two cycles of durvalumab (8 weeks). Subjects who do not remain on the study up to this time for reasons other than DLT will be replaced with another subject at the same dose level. Grading of DLTs will follow the guidelines provided in the Common Terminology Criteria for Adverse Events (CTCAE) version 4.03.

A DLT will be defined as any Grade 3 or higher toxicity that occurs during the DLT evaluation period. Toxicity that is clearly and directly related to the primary disease or to another etiology is excluded from this definition. The following will be DLTs:

- Any Grade 4 irAE
- Any \geq Grade 3 colitis
- Any Grade 3 or 4 noninfectious pneumonitis irrespective of duration
- Any Grade 2 pneumonitis that does not resolve to \leq Grade 1 within 3 days of the initiation of maximal supportive care
- Any Grade 3 irAE, excluding colitis or pneumonitis, that does not downgrade to Grade 2 within 3 days after onset of the event despite optimal medical management including systemic corticosteroids or does not downgrade to \leq Grade 1 or baseline within 14 days
- Liver transaminase elevation $> 5 \times$ ULN or total bilirubin $> 5 \times$ ULN
- Bone marrow findings consistent with myelodysplastic syndrome/acute myeloid leukemia
- Any \geq Grade 3 non-irAE, except for the exclusions listed below

The definition excludes the following conditions:

- Grade 3 fatigue lasting \leq 7 days
- Grade 3 endocrine disorder (thyroid, pituitary, and/or adrenal insufficiency) that is managed with or without systemic corticosteroid therapy and/or hormone replacement therapy and the subject is asymptomatic
- Grade 3 inflammatory reaction attributed to a local antitumor response (e.g., inflammatory reaction at sites of metastatic disease, lymph nodes, etc)
- Concurrent vitiligo or alopecia of any AE grade
- Grade 3 infusion-related reaction (first occurrence and in the absence of steroid prophylaxis) that resolves within 6 hours with appropriate clinical management
- Grade 3 or 4 neutropenia that is not associated with fever or systemic infection that improves by at least 1 grade within 3 days. Grade 3 or Grade 4 febrile neutropenia will be a DLT regardless of duration or reversibility
- Grade 3 or 4 lymphopenia

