Where toxicity reoccurs following re-challenge with olaparib, and where further dose interruptions are considered inadequate for management of toxicity, then the patient should be considered for dose reduction or must permanently discontinue treatment with olaparib. Dose de-escalation will be to 250 mg BID and then to 200 mg BID if needed.

Treatment must be interrupted if any NCI-CTCAE grade 3 or 4 adverse event occurs which the Investigator considers to be at least possibly related to administration of olaparib.

Management of anemia

Adverse events of anemia CTCAE grade 1 or 2 (Hemoglobin (Hb) > 8 g/dL) should be investigated and managed as deemed appropriate by the investigator with or without interruption of study drug or change in dose, taking into account previous history of anemia. Common treatable causes of anemia (e.g., iron, vitamin B12 or folate deficiencies and hypothyroidism) should be excluded. In some cases, management of anemia may require blood transfusions. However, if a patient develops anemia CTCAE grade 3 (Hb < 8 g/dL) or worse, study treatment should be interrupted for up to maximum of 4 weeks to allow for bone marrow recovery and the patient should be managed appropriately. Study treatment can be restarted at the same dose if Hb has recovered to > 10 g/dL. Any subsequently required anemia related interruptions, considered likely to be dose related, or coexistent with newly developed neutropenia, and or thrombocytopenia, will require study treatment dose reductions by 250 mg bd as a first step and to 200 mg bd as a second step.

If a patient has been treated for anemia with multiple blood transfusions without study treatment interruptions and becomes blood transfusion dependent as judged by investigator, study treatment should be permanently discontinued.

Management of neutropenia and leukopenia

Adverse event of neutropenia and leukopenia should be managed as deemed appropriate by the investigator with close follow up and interruption of study drug if CTC grade 3 or worse neutropenia occurs. Primary prophylaxis with Granulocyte colony-stimulating factor (G-CSF) is not recommended, however, if a patient develops febrile neutropenia, study treatment should be stopped and appropriate management including G-CSF should be given according to local hospital guidelines. Please note that G-CSF should not be used within at least 24 h of the last dose of study treatment.

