6.8 Treatment Discontinuation

Upon treatment discontinuation all end of treatment evaluations and tests will be conducted. All participants who discontinue due to an AE must be followed until the event resolves or stabilizes. Appropriate medical care should be provided until signs and symptoms have abated, stabilized, or until abnormal laboratory findings have returned to acceptable or pre-study limits. The final status of the AE will be reported in the participant’s medical records and the appropriate eCRF.

An individual subject will not receive any further investigational product if any of the following occur in the subject in question:

1. Withdrawal of consent or lost to follow-up.
 - a. If consent is withdrawn, the subject will not receive any further investigational product or further study observation.
2. Adverse event that, in the opinion of the investigator or the sponsor, contraindicates further dosing
3. Subject is determined to have met one or more of the exclusion criteria for study participation at study entry and continuing investigational therapy might constitute a safety risk.
4. Pregnancy or intent to become pregnant.

5. Any AE that meets criteria for discontinuation as defined in Section 10.1.
6. Adverse Event or DLT that, in the opinion of the Investigator, contraindicates further dosing (See Section 6.4 for definition of DLT).
7. Grade ≥ 3 infusion reaction.
8. Subject noncompliance that, in the opinion of the investigator or sponsor, warrants withdrawal; e.g., refusal to adhere to scheduled visits.
9. Initiation of alternative anticancer therapy including another investigational agent.
10. Confirmation of PD and investigator determination that the subject is no longer benefiting from treatment.
11. Development of intercurrent, non-cancer related illnesses that prevent either continuation of therapy or regular follow up.

Subjects who are permanently discontinued from further receipt of investigational product, regardless of the reason (withdrawal of consent, due to an AE, other), will be identified as having permanently discontinued treatment.

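### The DLT-evaluable definition in Section 12.3 leaves out a patient whose DLT was managed by a long olaparib hold while she stayed on study, and Section 4.3 allows her to be replaced

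*Combined protocol and SAP*

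**What the plan says.** Section 12.3 gives two routes into the DLT-evaluable set. The first is full exposure: "All patients who receive at least two cycles of durvalumab + tremelimumab and 8 weeks of olaparib treatment", with the corresponding safety assessments. The second is leaving early: "all patients who discontinue the study prematurely due to DLT are considered fully evaluable per protocol for DLT". It then adds a dose condition, that patients must have received "at least 75% of the planned dose of olaparib during the DLT evaluation period (except for patients who discontinued prematurely due to DLT".

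Four other sections bear on this:

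- **Section 6.4** sets an 8-week window. It makes any non-immune event of Grade 3 or higher a DLT unless it is on an exclusion list. Anemia is not on that list.
- **Section 6.5** requires interruption for any Grade 3 or 4 event possibly related to olaparib. For Grade 3 or worse anemia, "study treatment should be interrupted for up to maximum of 4 weeks to allow for bone marrow recovery", after which the same dose may be resumed once hemoglobin recovers.
- **Section 6.8** does not end treatment for every DLT. It lists an "Adverse Event or DLT that, in the opinion of the Investigator, contraindicates further dosing".
- **Section 4.3** says: "Patients who are not considered fully evaluable per protocol for the primary objective of safety and tolerability may be replaced". It repeats the 75% requirement with no DLT exception. Its mandatory replacement sentence covers only patients who leave for reasons other than DLT.

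No section makes a patient evaluable simply because she had a DLT.

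**The concern.** The reason to require adequate exposure is to stop an under-dosed patient without toxicity from being counted as evidence of safety. A patient who has already had a DLT has supplied her information, so her later exposure is irrelevant. Section 12.3 recognises this only when she leaves. If she is held and stays, the DLT itself is what takes her below 75%, and the rule can remove the event it is meant to count.

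Holding rather than stopping is an ordinary course. Section 1.3.2.4 reports that adverse reactions on olaparib led to interruption in 40% and discontinuation in 7% of one population, and in 26% and 9% of another. Those are whole-treatment monotherapy figures at a different dose and formulation, not DLT rates. They show only that interruption is the commoner outcome.

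At stake is the Phase I primary result. Section 12.3 defines the MTD by an observed DLT incidence below 33%, and Section 6.3 acts on more than one DLT in six patients.

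**Working it through.** The plan states no derived figure for this rule, so there is nothing to reproduce. Its two decision rules agree with each other: 1/6 = 16.7% is below 33%, and 2/6 = 33.3% is not.

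**1. When does a hold take a patient below 75%?** Inputs: 8 weeks = 56 days (Section 6.4); 75% (Section 12.3); holds of up to 28 days for anemia, and 14 days per occasion with repeats allowed for olaparib generally (Section 6.5).

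Fraction received = (56 − days held inside the window) / 56.

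| Days held in window | Fraction received | Meets 75%? |
|---|---|---|
| 14 | 42/56 = 75.0% | yes |
| 15 | 41/56 = 73.2% | no |
| 21 | 35/56 = 62.5% | no |
| 28 | 28/56 = 50.0% | no |

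Two 14-day interruptions also total 28 days, giving 50%. For a 28-day hold starting on day d, days lost in the window = min(28, 56 − d + 1). At d = 42 that is 15 days (73.2%, fails); at d = 43 it is 14 days (75.0%, passes).

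This takes planned dose to include the held days. Section 12.3 does not define the term, but the compliance formula in Appendix J divides by pills scheduled.

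**2. Where does each patient fall?**

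| Patient | Full exposure and 75%? | Discontinued because of DLT? | Evaluable? |
|---|---|---|---|
| DLT, leaves because of it | not required | yes | yes |
| DLT, held 14 days or less, stays | 75% met | no | yes, if the hold still counts as 8 weeks of olaparib |
| DLT, held more than 14 days in window, stays | no | no | **no; may be replaced** |

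**3. Effect on the decision.** Two DLTs in six patients is 33.3% and fails. If one DLT patient is dropped and her replacement has no DLT, the count is 1/6 = 16.7% and passes. That takes seven treated patients to reach six evaluable.

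**4. Illustrative size.** Let p be the true DLT rate and f the share of DLT patients dropped and replaced. The documents give neither, so both are assumed. The rate among evaluable patients is p′ = p(1 − f)/(1 − pf). The chance of at most one DLT in six is (1 − p′)⁶ + 6p′(1 − p′)⁵. For p = 0.33 and f = 0.25, p′ = 0.2475/0.9175 = 0.270 and the chance is 0.488.

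| p | f = 0 (any DLT counts) | f = 0.25 | f = 0.50 |
|---|---|---|---|
| 0.20 | 0.655 | 0.758 | 0.863 |
| 0.30 | 0.420 | 0.550 | 0.713 |
| 0.33 | 0.358 | 0.488 | 0.661 |
| 0.40 | 0.233 | 0.351 | 0.534 |

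The sizes depend on the assumed f. The direction does not: dropping DLT patients cannot raise the count.

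**The case against.** The strongest reply concerns consequences. Section 4.1 reports six patients **treated**, not six evaluable, at the 250 mg level "with no dose limiting toxicities observed". A dropped and replaced DLT patient would also have been treated there, which would mean at least seven. Taken at its word, the statement leaves 6 − 6 = 0 such patients at the dose carried into Phase II. An under-count at 300 mg would have favoured keeping 300 mg, so it cannot explain the move down to 250 mg. Phase I is complete, and the Phase II part of Table 1 lists DLTs as not applicable. All of this stands.

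The route is also narrow. Four weeks is a maximum, and replacement is permitted, not required. Section 6.3 counts DLTs in six patients without mentioning evaluability, so an investigator might well have counted her anyway. Appendix G discontinues the study regimen for a Grade 3 non-immune event that neither falls to Grade 2 or lower within 7 days nor resolves to Grade 1 or baseline within 14 days. Many prolonged DLTs would then end treatment and arguably enter the exempt group. This narrows the gap without closing it. Anemia that reaches Grade 2 within 7 days but takes more than 14 days to reach the hemoglobin level for restart in Section 6.5 still falls through.

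Nor is the event hidden. The safety set includes her, adverse events are listed per patient, and Phase I was reviewed at program meetings with minutes sent to the IRB. But the MTD and the 3+3 decision use the DLT count, not the safety listing.

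**Conclusion.** The defect in the wording is real and of moderate severity. Under Section 12.3 as written, a patient with a DLT who is held for more than 14 days inside the 56-day window and stays on study meets neither route to evaluability. Section 4.3 then permits, but does not require, her replacement. Any resulting bias in the DLT count is downward. This rests on the literal text and on planned dose including held days; the probabilities above rest on assumed p and f and show only the mechanism.

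A reader might infer that DLTs were in fact removed, or that the choice of 250 mg for Phase II is unsafe or unsupported. The documents do not support either inference. They report six treated at 250 mg with no DLTs, and nothing shows that any patient was dropped. What remains open is the DLT count at 300 mg, which the documents do not report, and confirmation that nobody was replaced at either level.

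**What to change.** 1. In Section 12.3, state that any patient with a DLT in the 8-week window is DLT-evaluable, whatever amount of study drug she received and whether or not she discontinued. The two-cycle, 8-week and 75% olaparib criteria then apply only to patients without a DLT.
2. In Section 4.3, state that a patient with a DLT is not replaced.
3. Report Phase I DLTs by olaparib level under this rule, listing every treated patient and any replaced patient with the reason.

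The cost is two sentences of protocol text and one re-tabulation of existing data, with no new patients or procedures. The downside is that the reported DLT rate could be less favourable.

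This changes the analysis set only; no dose or hold rule is proposed. The sponsor should reconcile the anemia hold in Section 6.5 with the Grade 3 non-immune discontinuation rule in Appendix G, because together they determine which patients stay on study after a DLT.
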